5.4.3 Exposure

Duration of exposure [weeks] will be calculated as

$$\frac{\text{Date of last trial drug intake} - \text{Date of first trial drug intake [days]} + 1 \text{ day}}{7}$$

The day of first trial drug intake will only be counted as a half day if the intake time was 2:30 p.m. or later. The day of last nintedanib intake will only be counted as a half day, assuming that only the morning dose was administered.

Treatment interruptions will not be subtracted. Duration of exposure will be summarised as continuous variable and in categories [weeks]:

- ≤2 (14 days)
- >2 to 6 (42 days)
- >6 to 12 (84 days)
- >12 to 24 (168 days)
- >24 to 36 (252 days)
- >36 to 52 (364 days)
- >52 to 64 (448 days)
- >64 to 76 (532 days)
- >76 to 88 (616 days)
- >88 to 104 (728 days)
- >104 to 116 (812 days)
- >116 to 128 (896 days)
- >128 to 140 (980 days)
- >140 to 156 (1092 days)
- >156

Duration of exposure on dose assigned according to weight range [weeks] will be calculated as

$$\frac{\text{Sum of durations on-treatment with dose effectively taken according to weight range [days]}}{7}$$

Duration of exposure on dose reduced due to AE [weeks] will be calculated as

$$\frac{\text{Sum of durations on-treatment with reduced dose effectively taken due to AE [days]}}{7}$$

7

Calculating the duration of exposure on dose assigned according to weight range and on dose reduced due to AE, time periods with treatment interruptions as well as on dose reduced due to other reasons will be excluded. Both durations will be summarised as continuous variable and in categories [weeks] as defined for duration of exposure [weeks] above.

In case the weight of the patient on reduced dose reduces in a way to match this lower dose level, the duration of exposure on reduced dose ends.

Summary of dose changes and treatment interruptions will be presented, containing

- Number of patients with at least one dose reduction
- Number of dose reductions per patient in categories (0; 1; 2; >2)
- Total number of dose reductions
- Reasons for dose reduction
- Number of patients with at least one dose increase
- Total number of dose increases
- Reasons for dose increase
- Number of patients with at least one interruption
- Number of interruptions per patient in categories (0; 1; 2; >2)
- Total number of interruptions
- Reasons for interruption
- Number of patients with at least one dose reduction or interruption

Duration of interruptions [days] will be calculated as

$$\text{Sum of all treatment interruption durations [days]}$$

Total dose [g] will be calculated as

$$\text{Sum of durations of exposure on } x \text{ g [days]} * 2 * x \text{ g,}$$

with x in 0.025, 0.05, 0.075, 0.1, 0.15 and summarised as continuous variable.

Dose intensity [%] will be calculated as the amount of drug actually administered divided by the amount of drug that would have been administered, i.e. dose xx mg bid (depending on the body weight) during the planned treatment period (or until study discontinuation), multiplied by 100%. Dose intensity will be summarised as continuous variable and in categories [%]:

- ≤ 30
- > 30 to 50
- > 50 to 90
- > 90 to < 100
- ≥ 100

Exposure-related time-to-event analyses will be performed for the following items:

- Time to first dose reduction (not due to weight-based adjustment) [days]^[1]
- Time to first treatment interruption [days]
- Time to premature treatment discontinuation [days]

^[1] Will only be calculated for patients who started the trial on full dose according to their weight bin at baseline.

Time-to-event [days] for exposure-related analyses is derived based on first trial drug intake as

$$\text{Date of event/censoring} - \text{Date of first trial drug intake [days]} + 1 \text{ day}$$

For the above mentioned time-to-event analyses patients with no such event occurred during the trial will be censored according to the mechanism for censoring as described in [Table 5.4.3: 1](#).

Table 5.4.3: 1 Censoring rules for exposure-related time-to-event analyses

Rule #	Situation	Outcome (Event/Censored)	Date of event/censoring
1	Patient had a documented event and the date of the event is known	Event	Earliest date of event
2	Patient had a documented event and the date of the event is unknown	Event	Imputed date of event (as defined in Section 6.6.3.3)
3	Patient had no documented event and already terminated trial drug (last intake on End of treatment eCRF page available)	Censored	Date of last trial drug intake
4	Patient neither had a documented event nor terminated trial drug permanently (only applicable for potential interim analyses)	Censored	Date of interim data snapshot

These times will also be summarised in categories [weeks] as defined for duration of exposure [weeks] above.

5.4.4 Liver enzyme and bilirubin elevations

Liver enzyme and bilirubin elevations will be reported using the following definitions:

- (ALT and/or AST ≥ 3 fold ULN) and bilirubin ≥ 2 fold ULN ^[1]
- ALT ≥ 5 fold ULN and/or AST ≥ 5 fold ULN
- ALT ≥ 3 fold ULN and/or AST ≥ 3 fold ULN

^[1] within a time window of 30 days i.e. the elevation of bilirubin should appear within 30 days after the elevation of AST and/or ALT

The proportion of patients presenting signs of hepatic injury will be summarised, based on the following definition for signs of hepatic injury:

- ALT and/or AST ≥ 8 fold ULN
- ALT and/or AST ≥ 3 fold ULN and total bilirubin ≥ 2 fold ULN ^[2]
- ALT and/or AST ≥ 3 fold ULN and unexplained INR > 1.5 ^[2]
- ALT and/or AST ≥ 3 fold ULN and unexplained eosinophilia ($> 5\%$) ^[2]

- ALT and/or AST ≥ 3 fold ULN and appearance of fatigue, nausea, vomiting, right upper abdominal quadrant pain or tenderness, fever and/or rash within +/- 7 days of the abnormal ALT and/or AST laboratory test result (please refer to [Table 10.5: 1](#) for the list of relevant MedDRA preferred terms to support the derivation of a potential hepatic injury)

^[2] in the same blood draw sample

In addition, maximum individual elevations based on worst value on treatment will be defined as:

- ≥ 3 fold ULN; ≥ 5 fold ULN; ≥ 8 fold ULN for AST and ALT and AST and/or ALT
- ≥ 1.5 fold ULN; ≥ 2 fold ULN for Bilirubin
- ≥ 1.5 fold ULN; ≥ 2 fold ULN for alkaline phosphatase (ALK)
- ≥ 3 fold ULN for Gamma-Glutamyl-Transferase (GGT)

Note: ULN refers to the Upper Limit of Normal from the central or local laboratory analysing samples.

5.4.4.1 Time-to-event analyses for liver enzyme elevations

- Time to liver enzyme and bilirubin elevation (ALT and/or AST $\geq 3xULN$ and bilirubin $\geq 2xULN$)
- Time to liver enzyme elevation (ALT and/or AST $\geq 5xULN$)
- Time to liver enzyme elevation (ALT and/or AST $\geq 3xULN$)

Time to first occurrence of the above described liver enzyme elevations [days] is derived based on first trial drug intake as

$$\text{Date of event/censoring} - \text{Date of first trial drug intake [days]} + 1 \text{ day.}$$

Patients with no such event documented will be censored according to the mechanism for censoring as described in [Table 5.4.4.1: 1](#).

Table 5.4.4.1: 1 Censoring rules for time to first occurrence of liver enzyme elevations

Rule #	Situation	Outcome (Event/Censored)	Date of event/censoring
1	Patient had a documented event before permanent trial drug discontinuation (or within the 28 days after permanent trial drug discontinuation)	Event	Earliest date of event
2	Patient had no documented event before permanent trial drug discontinuation (or within the 28 days after permanent trial drug discontinuation).	Censored	Earliest date of 
 • last trial drug intake + 28 days, • derived date of last contact when patient was known to be alive, • date of death.
3	Patient neither had a documented event nor terminated trial drug permanently (only applicable for potential interim analyses)	Censored	Date of interim data snapshot

These times will also be summarised in categories [weeks] as defined for duration of exposure [weeks] in [Section 5.4.3](#).

5.4.5 Vital signs

Weight minimum relative change from baseline will be summarised as continuous variable and in categories:

- Relative decrease of more than 10% (excl.)
- Relative decrease of between 5% (excl.) and 10% (incl.)
- Relative decrease of between 0% (excl.) and 5% (incl.)
- Relative increase ($\geq 0\%$)

6. GENERAL ANALYSIS DEFINITIONS

6.1 TREATMENT(S)

For treatment specifications, please refer to CTP Section 4.

The different periods of interest, as per CTP flow chart are as described in [Table 6.1: 1](#).

Table 6.1: 1 Periods of interest for the analysis

Period	Start date	End date (excluded)
Screening period	Informed consent	First trial drug intake
Treatment period	First trial drug intake (or re-start of treatment, if interruption)	Last trial drug intake (or day before start of interruption, if interruption) + 1 day
Off-treatment period (optional ^[a])	Start of interruption	Re-start of treatment
Residual effect period (REP)	Last trial drug intake + 1 day	Last trial drug intake + 28 days + 1 day
Follow-up period (optional ^[a]) ^[b]	Last trial drug intake + 29 days	Start of post-study period
Post-study period (optional ^[a])	Latest of 
 • Last trial drug intake + 29 days • End of study participation (from End of Study eCRF page) + 1 day 	

^[a] This period is optional insofar as it does not necessarily exist for all patients.

^[b] This period is only created if last trial drug intake took place more than 28 days before trial completion (last contact date as collected on the end of study eCRF page), or for patients having prematurely discontinued the treatment and still continuing the trial.

For patients who died during the trial, periods with above defined start date after date of death do not exist and last existing period is defined until date of death plus one day only.

6.2 IMPORTANT PROTOCOL DEVIATIONS

Handling of iPDs in analysis is included in the DV domain specifications and stored within the TMF in EDMS.

6.3 INTERCURRENT EVENTS

[figure not shown]
The expected intercurrent event of interest in this trial is treatment discontinuation. The strategy for handling intercurrent events in this trial is While-on-Treatment. For more details see CTP Section 7.2.2.

[figure not shown]
Any intercurrent events that are not listed will be decided by review based on the general principle outlined.

6.4 SUBJECT SETS ANALYSED

- Screened set (SCS):
This patient set includes all patients having signed informed consent.
- Treated set (TS):
This patient set includes all patients who were dispensed study medication and were documented to have taken at least one dose of investigational treatment.
- Pharmacokinetic set (PKS):
This patient set includes all patients from the Treated Set (TS) with at least one evaluable PK plasma concentration.

All evaluations for PK endpoints will be based on the PKS. All other analyses will be based on the TS, except for disposition which is based on the SCS.

[figure not shown]

6.6 HANDLING OF MISSING DATA AND OUTLIERS

In general, missing data will not be imputed. Exceptions are detailed in the subsequent subsections.

6.6.1 Primary endpoint

Missing or incomplete AE dates will be imputed according to BI standards (see “Handling of missing and incomplete AE dates”) ([7](#)).

6.6.2.2 Time-to-event endpoints

[figure not shown]
In the analyses of the time-to-event endpoints, missing or incomplete data will be managed by standard survival analysis techniques (i.e. censoring). If a patient has no event then he or she will be censored as described in [Section 5.3.2](#).

A missing or incomplete date of death will be imputed/completed that the derived date is the earliest possible date which is on or after date of onset of the fatal AE, and on or after first trial drug intake (in case this AE is treatment-emergent), and on or after derived date of last contact as defined in [Section 5](#).

For the time to first respiratory-related hospitalisation, or time to first acute ILD exacerbation, in case of partially missing dates, the following imputation will be done:

- If day is missing, then imputed day will be the 15th of the month
- If day and month are missing, then imputed date will be the 1st of July of the (non-missing) year
- If year is missing, date will not be imputed

The same imputation rule will be applied for the time to first dose reduction in case of partially missing start date.

[figure not shown]

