6.6.3.3.2 Treatment interruptions

[figure not shown]
For the definition of off-treatment periods an incomplete start or end date for a treatment interruption will be imputed the same way as specified for time-to-event analyses in [Section 6.6.2.2](#). For duration of interruption no imputation will be applied, i.e. interruptions with missing or incomplete start or end date will have duration missing. Overall duration of interruptions per patient will be missing in these cases as well.

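### The SAP's mid-month and mid-year date imputation has no floor at first dose and no start-before-end check, so it can give zero or negative times and off-treatment periods that end before they start

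*SAP*

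**What the plan says.** SAP Section 6.6.2.2 gives one rule for partially missing dates in time to first respiratory-related hospitalisation and time to first acute ILD exacerbation: "If day is missing, then imputed day will be the 15th of the month" and "If day and month are missing, then imputed date will be the 1st of July of the (non-missing) year". A date with no year is not imputed. The section then widens the scope: "The same imputation rule will be applied for the time to first dose reduction in case of partially missing start date".

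Section 6.6.3.3.2 carries the rule to interruptions: "For the definition of off-treatment periods an incomplete start or end date for a treatment interruption will be imputed the same way". It does not carry it to the reported duration, since "interruptions with missing or incomplete start or end date will have duration missing".

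Two other parts of the SAP use these dates. Section 5.4.3 sets the clock: "Time-to-event [days] for exposure-related analyses is derived based on first trial drug intake as" the event or censoring date minus the date of first intake, plus one day. Table 6.1: 1 ends a treatment period at the start of an interruption, runs an off-treatment period to the re-start, and opens the next treatment period there.

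No floor at first intake, cap at death or ordering check is written for this rule. Other imputed dates do carry bounds. An imputed date of death must fall on or after fatal AE onset, last contact and, for a treatment-emergent AE, first intake (6.6.2.2). An imputed last intake must fall on or before death and last contact (6.6.3.3.1).

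**The concern.** A fixed calendar date ignores what else is known about the patient. If a dose reduction occurs in the month or year of first dose, the imputed date can fall before treatment began, and the Section 5.4.3 formula then returns zero or a negative number. If one end of an interruption is partial, the imputed date can land on the wrong side of the known one. The off-treatment period then has negative length and the two neighbouring treatment periods overlap.

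The trial expects about 50 to 60 patients, analysed in two groups, so even one impossible time would be visible in a Kaplan-Meier summary or a listing. A programmer who meets one must then choose whether to clip it, drop it or set it to missing. The SAP does not say which, and the choices give different results.

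**Working it through.** The documents state no figure on this point, so there is nothing to reproduce. The check applies the rules literally. The patient dates are illustrative assumptions.

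**1. Time to first dose reduction.** Formula (SAP 5.4.3): time = imputed event date - first intake + 1.
- First dose 20 March, event known only as March: 15 March - 20 March + 1 = -5 + 1 = -4 days.
- First dose 1 October, event known only by that year: 1 July - 1 October + 1 = -92 + 1 = -91 days.

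In general, with the day missing and first dose on day d of the same month, time = 15 - d + 1 = 16 - d. This is zero at d = 16 and negative from d = 17. In a 365-day year, the first-dose dates with d of 17 or more number 7 × 15 + 4 × 14 + 12 = 173, so 173/365 = 47.4% give a negative time. Adding the twelve 16ths, 185/365 = 50.7% give zero or less. With day and month missing, 182 of 365 first-dose dates give a negative time and 183 give zero or less.

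These are shares of calendar dates, not probabilities that an event is affected, because a late first dose leaves few days for an event in the same month. In a 30-day month there are 30 × 31/2 = 465 pairs with the event on or after first dose. Of these, 14 × 15/2 = 105 have first dose on the 17th or later, so with all pairs equally likely the share is 105/465 = 22.6%.

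**2. Off-treatment periods.** Take the imputed end as the re-start date. An interruption starting 20 May with its end known only as May ends on 15 May: 15 - 20 = -5 days. The next treatment period then opens five days before the previous one closes.

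The shares below assume a start date spread evenly over 365 days, and they are conditional on the date being partial:

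| Length (days) | End day missing: end before start | Start day missing: start after end | End day and month missing: end before start |
|---|---|---|---|
| 3 | 40.8% | 36.2% | 49.3% |
| 7 | 27.7% | 23.0% | 48.2% |
| 14 | 4.9% | 0% | 46.3% |
| 28 | 0% | 0% | 42.5% |
| 56 | 0% | 0% | 34.8% |

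Check of the first row. The end falls before the start when the start is on the 16th or later and the re-start is in the same month: 7 × 13 + 4 × 12 + 10 = 149, and 149/365 = 40.8%. The start falls after the end when the start is on the 11th or earlier: 12 × 11 = 132, and 132/365 = 36.2%. Lengths up to 56 days are relevant because Protocol Table 4.2.1:1 sets maximum interruptions of 4 or 8 weeks. The problem runs in both directions, so a check on the end date alone would not be enough.

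**3. Death.** An event known only as March in a patient who died on 5 March is dated 15 March, ten days after death.

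**4. With bounds added.** The first two cases become day 1, the 20 May interruption becomes 0 days, and the event in step 3 moves to 5 March.

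**The case against.** The strongest counter-argument is that this will rarely happen and matters little when it does. Protocol Section 8.3.1 makes onset dates mandatory for adverse and outcome events. Dose reductions between visits are registered in IRT (Protocol 4.1.4). Visits are 12 to 16 weeks apart for most of the trial, so an event known only by year is improbable. A negative time also needs the event to fall in the month or year of first dose. All endpoints are exploratory and no test is planned. All of this stands, and it keeps the point minor. It does not make the rule right where the rule is used.

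A reader might infer more than the documents support:
- *That the SAP contradicts itself.* The death and last-intake rules show that bounds were considered elsewhere. They govern different dates, and neither conflicts with this rule. It is under-specified.
- *That negative interruption durations will be reported.* They will not: Section 6.6.3.3.2 leaves the duration missing when either date is incomplete. The defect is confined to the off-treatment periods.
- *That nothing guards against dates after death.* The note to Table 6.1: 1 drops or truncates analysis periods at death. Only the imputed event date itself lacks a cap.
- *That events can fall after their own censoring date.* Under Table 5.4.3: 1 a patient with a documented event counts as an event even if the date is unknown, and is not censored.
- *That the primary endpoint is at risk.* AE dates follow a separate sponsor standard (6.6.1), and the on-treatment window runs from first intake to last intake plus 28 days regardless of interruptions (7.8).

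For respiratory hospitalisation and ILD exacerbation, the definitions and censoring are in SAP Section 5.3.2, which is not visible in the public text. A bound there cannot be excluded.

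**Conclusion.** The gap is real and minor. For time to first dose reduction, the visible rules permit zero or negative times. For interruptions with a partial date, they permit off-treatment periods that end before they start. Time to first interruption would share the first problem if the interruption rule is used for it: Table 5.4.3: 1 sends unknown event dates to Section 6.6.3.3, and the only interruption rule there is the one for off-treatment periods.

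For hospitalisation and exacerbation the conclusion depends on Section 5.3.2. The worked dates are illustrative, and the documents do not say how often dates will be partial, so no expected count can be given. The effect is limited to descriptive time-to-event summaries, the definition of analysis periods and any exposure derivation that uses those periods.

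**What to change.** Add to SAP Sections 6.6.2.2 and 6.6.3.3.2:

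*For events known to have occurred on treatment, an imputed date earlier than first trial drug intake is set to the date of first intake; an imputed event date may not be later than the date of death. For interruptions, an imputed start may not be later than a known end, and an imputed end may not be earlier than the start; in either case the imputed date is set to the paired date.*

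If both interruption dates are partial, impute the start first and then check the end against it. A cap at last contact is best left out: the derived last contact date in Section 5 already includes dose-change and interruption dates, so that cap would be partly circular.

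While the text is open, correct the pointer in Table 5.4.3: 1. It sends unknown event dates to Section 6.6.3.3, but the dose-reduction rule is in 6.6.2.2.

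The cost is two SAP sentences, one cross-reference and a min/max step in the derivation code. No endpoint changes, and only impossible values are replaced.

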6.6.3.3 Exposure

6.6.3.3.1 Permanent trial drug discontinuation

A missing or incomplete date of last trial drug intake will be imputed that the derived date is the latest possible date which is on or before date of death, and on or before last contact date from End of Study eCRF page.

6.6.3.3.2 Treatment interruptions

[figure not shown]
For the definition of off-treatment periods an incomplete start or end date for a treatment interruption will be imputed the same way as specified for time-to-event analyses in [Section 6.6.2.2](#). For duration of interruption no imputation will be applied, i.e. interruptions with missing or incomplete start or end date will have duration missing. Overall duration of interruptions per patient will be missing in these cases as well.

6.7 BASELINE, TIME WINDOWS AND CALCULATED VISITS

For roll-over patients Visit 1 and Visit 2 should be conducted on the same day and should, if possible, occur the same day as the EoT Visit of the parent trial to avoid any treatment interruption. In this case, assessments conducted as part of EoT of the parent trial are not repeated for the extension trial and results are only reported in the parent trial database. Therefore, the last available result in parent trial will be considered as baseline value for the extension trial if still meeting the baseline criteria as defined in this section.

As a general rule, the last assessment/measurement observed prior to first trial drug intake will be used as baseline. If the time of the assessment/measurement was not captured, and it was on the same day on which trial medication started, it will be assumed that it was taken prior to the intake of trial medication. Similarly, if no time is reported for start of trial medication it will be assumed that all trial procedures on that day happened before trial drug intake.

Visit windowing will be performed as described in the following tables, in order to assign data to the relevant study visit based on the actual day of the assessment. Data will be

analysed using the re-assigned visits in the statistical tables. However, in the patient data listings, all visits performed will be displayed (even if outside time-window), along with the re-assigned visit.

If after windowing of visits at baseline, two or more values fall within the same baseline interval, then the last value prior to first trial drug intake will be taken into account. If after windowing of post-baseline visits, two visits fall in the same interval, then the measurement closest to the planned visit will be taken into account. If only on-treatment values are to be considered (e.g. vital signs, laboratory data), this rule will be applied to on-treatment assessments only. In case two measurements are equidistant from the planned visit, then the last one will be picked.

Table 6.7: 1 Time windowing rules for [REDACTED] vital signs (syst. and diast. blood pressure, pulse rate, weight) and laboratory tests ([REDACTED])

Time window of actual day ^[1,2]			Allocated to		
Start day	End day (included)	Length of the time-window [days]	Visit number	Visit name	Planned day of the visit
-35	1	36	2	Baseline	1
2	50	49	3	2 weeks	15
51	127	77	4	12 weeks	85
128	211	84	5	24 weeks	169
212	309	98	6	36 weeks	253
310	407	98	7	52 weeks	365
408	491	84	8	64 weeks	449
492	575	84	9	76 weeks	533
576	673	98	10	88 weeks	617
674	771	98	11	104 weeks	729
772	855	84	12	116 weeks	813
856	939	84	13	128 weeks	897
940	1037	98	14	140 weeks	981
1038	1135	98	15	156 weeks	1093

^[1] First trial drug intake date is taken into account as reference to calculate time windows.

^[2] For analyses of LDH as biomarker, values are only considered up to + 7 days after last trial drug intake.

Table 6.7: 2 Time windowing rules for height and body mass index

[figure not shown]
Time window of actual day ^[1]			Allocated to		
Start day	End day (included)	Length of the time-window [days]	Visit number	Visit name	Planned day of the visit
-35	1	36	2	Baseline	1
2	127	126	4	12 weeks	85
128	211	84	5	24 weeks	169
212	309	98	6	36 weeks	253
310	407	98	7)	52 weeks	365
408	491	84	8	64 weeks	449
492	575	84	9	76 weeks	533
576	673	98	10	88 weeks	617
674	771	98	11	104 weeks	729
772	855	84	12	116 weeks	813
856	939	84	13	128 weeks	897
940	1037	98	14	140 weeks	981
1038	1135	98	15	156 weeks	1093

[figure not shown]
^[1] First trial drug intake date is taken into account as reference to calculate time windows.

[figure not shown]
Table 6.7: 3 Time windowing rules for leg length

[figure not shown]
Time window of actual day ^[1]			Allocated to		
Start day	End day (included)	Length of the time-window [days]	Visit number	Visit name	Planned day of the visit
-35	1	36	2	Baseline	1
2	127	126	4	12 weeks	85
128	211	84	5	24 weeks	169
212	309	98	6	36 weeks	253
310	449	140	7	52 weeks	365
450	631	182	9	76 weeks	533
632	813	182	11	104 weeks	729
814	995	182	13	128 weeks	897
996	1177	182	15	156 weeks	1093

^[1] First trial drug intake date is taken into account as reference to calculate time windows.

